- A PHQ-9 score of ≥ 15 represents moderately severe depression. Subjects with a score of ≥ 15 at the Pre-Study Screening will be excluded from participating in the study and will be referred to a mental health provider.

Note: Question 9 on the PHQ-9 is a single screening question on suicide risk. If a subject answers yes to question 9, they are ineligible to continue with the study and will be immediately referred to a mental health provider for further assessment.

Once recruited subjects are on a stable dose of Suboxone or Subutex for 2 or more weeks, we will initiate one of three dose reduction strategies. We will compare tolerance in the same person to an alternating 1 mg vs 2 mg weekly reduction (Magnitude group, n=10). In a second group (Frequency group, n=10) we will compare tolerance in the same person to an alternating 2 mg reduction occurring weekly vs bi-weekly. All subjects in the Magnitude and Frequency groups will be on TID or QID dosing. In a third group (Dosing Group, n=10) we will compare tolerance to either the Magnitude or Frequency reduction schedule in women who are on a BID dosing regimen. The comparisons in these three groups will address those fundamental questions required for development of a rational dose reduction strategy. Each of these strategies addresses a specific question about maternal accommodation to the specified dose change. The dose reduction magnitude of 1 mg vs 2 mg and the frequency of reduction of weekly vs bi-weekly selected are based in large part on the work of Sigmon et al.⁴⁷ but larger and more frequent reductions could be considered. We chose this modest reduction strategy as we were concerned that more aggressive changes could lead to subject withdrawal and dissatisfaction. In the study of Sigmon et al.⁴⁷, only 50% of participants were opioid abstinent with the 4-week taper (i.e. 1.75 mg per week). We believe a slower taper regimen could improve upon this outcome. Table 1 provides an example of the dose reduction strategy assuming, as an example, a starting dose of 16 mg daily. Subjects on TID or QID dosing will be assigned to either the Frequency or Magnitude groups based on their current dosing. Subjects on BID dosing will be assigned to the Dosing group.

- Subjects assigned to the Frequency group will have dose reductions of 2 mg on alternating intervals of 1 and 2 weeks.
- Subjects assigned to the Magnitude group will have alternating reductions of 1 then 2 mg every week.

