- Subjects in the BID group will be assigned to the Dosing group. The Dosing group may follow the Magnitude (alternating 1 mg and 2 mg dose reductions weekly) or Frequency (2 mg dose reductions on alternating intervals of 1 and 2 weeks) dose reduction schedules.

In all groups, the alternating approach will continue until the subject is Suboxone or Subutex free or at the lowest dose tolerable. We appreciate that some subjects may not tolerate the recommended dose reduction especially at the lower doses. Subjects that experience withdrawal symptoms may be treated with ancillary medications such as Benadryl or clonidine. To minimize any risk of relapse, subjects who are intolerant to a given reduction will be allowed to go back to the last tolerated dose taken prior to the reduction. Visual Analog Scale (VAS) scoring will document their intolerance and this, combined with pharmacological data from the subject, will inform our development of an optimized pharmacological approach to dose reductions. After the subject has been on the higher dose for one week we will re-initiate the dose reduction strategy to which she was assigned. We will repeat this process one more time and if she remains intolerant to further dose reductions, we will not attempt further reductions but rather will maintain her on her current dose. If the subjects desires additional attempts at dose reduction, we will accommodate her request. At this time, she may elect to re-initiate the original dose reduction strategy or select an alternative reduction strategy. For all subjects, we will continue the surveillance approach we have in place throughout the pregnancy, delivery, and into the postpartum period.

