In all 3 groups, daily adherence, cravings and sleep measures will be compared within and across groups. During the Pre-Study Screening, we will explain the study to the subject and ask that she completes an Intake Questionnaire to better understand any previous experiences she may have had with opioid treatment or detox programs. We will also perform urine and blood testing to assure all entry criteria are fulfilled. Once consent is obtained, we will initiate a Suboxone or Subutex dose reduction schedule similar to the one shown in Table 1. To ascertain the impact of a dose change, all subjects will complete 4 daily VAS questionnaires similar to those used by Dunn et al. ⁴⁶ to assess withdrawal, cravings, sleep duration and sleep quality. The scales will range from a score of 0-10 for each question. Subjects that wish to be contacted via text will be sent a daily text with a link to the REDCap website where they can complete the VAS

questionnaire electronically throughout the dose reduction process. Subjects that are unable to receive daily text messages will be provided hard copies of the VAS questionnaire and instructed to return the completed forms to research staff at their next appointment. Clinic visits will occur weekly or biweekly at which time we will monitor plasma BUP+M, neurotransmitter and cotinine concentrations and perform a comprehensive urinary toxicology test. Additionally, at each clinic visit we will administer the Weekly Follow-up and Weekly Smoking and Alcohol Use questionnaires. We will also collect any completed VAS forms, if applicable, and perform COWS and Subjective Opioid Withdrawal Scale (SOWS) scores to assess current clinical and subjective symptoms of withdrawal and satiety. All subjects will receive psychosocial support, as needed. The timing of the subject's scheduled visits will be determined by their healthcare provider.

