Week 1	16	16	Refer to the appropriate dose schedule in the Frequency or Magnitude columns
Week 2	14	15	
Week 3	14	13	
Week 4	12	12	
Week 5	10	10	
Week 6	10	9	
Week 7	8	7	
Week 8	6	6	
Week 9	6	4	
Week 10	4	3	
Week 11	2	1	
Week 12	2	0	
Week 13	0	0	

e) Statistics

The outcome(s) of interest are the pharmacodynamic endpoints that reflect the acclimatization of the mu receptors and opioid-affected brain functions. Each subject in a group will undergo alternating treatments to minimize any between subject differences that would impact the response to the decrease in dose. In this study, we will rely on scores from the self-administered VAS questionnaires. We will determine both an average and highest value for each of the VAS questionnaires weekly. The average values over the 7 days of

that given dose from the VAS questionnaires will be combined to create a single score for each week. A similar approach will be taken for the highest rather than average values. Based on the study of Dunn et al ^{46,47}, the mean value for the withdrawal VAS questionnaire (scale 1-10) in non-pregnant subjects was 30 with a standard deviation of ~25. These values are estimates since graphs were provided but not tabular data. A difference of 25% in the VAS combined scores between any of the comparisons would seem clinically meaningful. Thus, a sample size of 10 in each group is sufficient to detect a difference in VAS scores between any of the comparison groups. The comparisons in the Frequency group will be VAS scores between the 1 vs 2 week reductions. The comparisons in the Magnitude group would be VAS scores between the 1 and 2 mg reductions. The comparison in the Dose group will be a comparison of the VAS scores during the 1 mg and 2 mg reductions. Also, VAS scores in the Dose group will be compared to the VAS scores in the Magnitude group both at the 1 and 2 mg reductions. The change in mu receptor sensitivity will be determined by comparing the BUP+M

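### Minor: the Dosing versus Magnitude comparison is between non-randomised groups of women and has no adjustment for dose; a mixed model with starting dose and pre-step dose would be a cheap improvement

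*Combined protocol and SAP*

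**What the plan says.** Section e) Statistics of the combined protocol and SAP gives three kinds of contrast on the weekly VAS scores.

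- Within women, Magnitude group: "The comparisons in the Magnitude group would be VAS scores between the 1 and 2 mg reductions". The same 1 versus 2 mg contrast is planned within the Dosing group.
- Within women, Frequency group: "The comparisons in the Frequency group will be VAS scores between the 1 vs 2 week reductions".
- Between women: "VAS scores in the Dose group will be compared to the VAS scores in the Magnitude group", at each step size.

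No model or covariate is named, and there is no rule for weeks at 0 mg. The reason given for the design is that "Each subject in a group will undergo alternating treatments to minimize any between subject differences". Section e) also relates weekly drug concentrations to VAS scores, but for mu receptor sensitivity and not to adjust these contrasts.

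Section d) Study Design sets the groups by existing regimen: "Subjects on BID dosing will be assigned to the Dosing group", while women on TID or QID go to Magnitude or Frequency. Dosing women may follow either schedule. Inclusion criterion 5 allows starting doses of 6 to 24 mg. Section d) also expects that "some subjects may not tolerate the recommended dose reduction especially at the lower doses".

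**The concern.** The plan itself expects tolerance to depend on dose, so a contrast that mixes steps taken at different doses can pick up dose as well as the factor of interest.

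Alternating steps removes stable differences between women from the within-woman contrasts. It does nothing for Dosing versus Magnitude. If BID women tend to start on lower or higher doses than TID or QID women, a raw VAS difference mixes dosing frequency with dose level. That contrast bears on research question 2, whether dosing frequency influences adherence during reduction.

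**Working it through.** **Inputs.** Table 1 schedules; even starting doses 6 to 24 mg (criterion 5); uninterrupted tapers. Pre-step dose is the daily dose just before a reduction. It is used rather than the dose after the step, which contains the step size. The last step, to 0 mg, is left out at first.

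**1. Table 1, Magnitude, 16 mg start.** Alternating 1 and 2 mg reproduces the printed column: 16, 15, 13, 12, 10, 9, 7, 6, 4, 3, 1, 0. Pre-step doses:
- 1 mg steps: 16, 13, 10, 7, 4; mean 50/5 = 10.0 mg.
- 2 mg steps: 15, 12, 9, 6, 3; mean 45/5 = 9.0 mg.

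Difference (2 mg minus 1 mg): -1.0 mg.

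**2. All even starts, within women.**
- Magnitude: -1.0 mg from 10, 16 and 22 mg, and +0.5 mg from the other seven. Average = (3 × -1.0 + 7 × 0.5)/10 = +0.05 mg.
- Frequency, steps labelled by their slot in the 1, 2, 1, 2 week sequence (2 week minus 1 week): 0 from 8, 12, 16, 20 and 24 mg, and -2.0 mg from 6, 10, 14, 18 and 22 mg. Average -1.0 mg. The sign reverses if steps are labelled by the interval that follows, and section e) does not say which is meant.

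**3. Between women, Magnitude schedule.** Mean pre-step dose from a 6 mg start is (6 + 5 + 3)/3 = 4.7 mg. From 24 mg it is 206/15 = 13.7 mg. Slope = (13.7 - 4.7)/(24 - 6) = 0.5 mg per mg of starting dose. The documents give no starting doses by group, so the gap has to be assumed: 2 to 6 mg in mean starting dose gives 1 to 3 mg in mean pre-step dose.

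**4. Does adding pre-step dose alone repair the group contrast?** Within a woman, pre-step dose is almost the same variable as taper week. From 6 mg, doses 6, 5, 3, 2 against weeks 1 to 4 give r = -7/√(10 × 5) = -0.99. The fitted dose slope is therefore largely a time trend, yet it would be used to correct a gap between women.

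Take an assumed 4 mg gap in mean starting dose, which is 2 mg in mean pre-step dose, and no true group effect. Differences are higher-start group minus lower-start group. The schedule removes (1 + 2)/2 = 1.5 mg a week on average.
- Symptoms rise 3 points per taper week. Week ≈ (S - d)/1.5, so VAS ≈ 2S - 2d, with S the starting and d the pre-step dose. Raw bias = 2 × 4 - 2 × 2 = +4. With d alone the slope is about -2, so the adjusted bias = 4 - (-2 × 2) = +8. With S also in the model it is 0.
- Symptoms follow absolute dose, VAS = -b·d. Raw bias = -2b. It is 0 with d in the model, with or without S.

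Simulations agree (10 versus 10 women, stop excluded, the same 4 mg gap, all inputs assumed). The ranges cover two separate runs:

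| Assumed driver of symptoms | Unadjusted | Pre-step dose only | Plus starting dose |
|---|---|---|---|
| Fraction of starting dose removed (40 points in total) | +0.7 to +1.3 | +5.0 to +5.7 | within about 1 |
| Taper week (3 points per week) | +3.1 to +4.3 | +7.2 to +8.1 | within about 1 |
| Absolute mg | -5.3 to -4.5 | +0.1 to +0.6 | within about 1 |

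**5. The step to 0 mg, only if that week is scored.** Let X be its excess over other weeks with the same label (not in the documents), and let every woman reach 0. Each woman's contrast moves by +X/k or -X/k, where k is her number of steps under that label. With one woman per even start and slot labels, the Magnitude shift is

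(1/2 + 1/3 - 1/4 + 1/4 + 1/5 - 1/6 + 1/6 + 1/7 - 1/8 + 1/8)/10 = +0.118X.

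Labelled by mg actually removed, the last steps from 8, 14 and 20 mg count as 1 mg and the shift is -0.004X. The Frequency shift averages 0. With ten women at random even starts, the 95% ranges are -0.02X to +0.25X (Magnitude, slot label) and -0.19X to +0.19X (Frequency).

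**6. Precision.** Standard errors in units of the weekly within-woman SD, one woman per even start. As written, against stop dropped and dose added: Magnitude 0.197 to 0.209 (+6%); Frequency 0.232 to 0.251 (+8%). The dose term alone, once the stop is out: 0.209 to 0.209 and 0.250 to 0.251 (under 1%).

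**The case against.** The strongest objection is to the obvious remedy. A single pre-step dose covariate is mostly a within-woman time trend and can increase bias in the very contrast that most needs protection. The documents do not say whether symptoms follow absolute dose, fraction removed or time, and the remark about lower doses fits all three. This stands, and it is why starting dose must be in the model.

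It can also be said that the within-woman contrasts are nearly balanced already, and that this is a pharmacodynamic study of ten women per group with no named test. Both points stand and keep the matter minor.

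A reader might infer that the step to 0 mg seriously distorts the 1 versus 2 mg or 1 versus 2 week results. With assumed rises of up to 60 points over the taper and a further 60 at 0 mg, and dose taken after the step, a 16 mg start can give -10 to +22.5 points against a target of 0.25 × 120 = 30. The documents supply none of those rises, and dose after the step contains the step size. Nor do they settle whether a week at 0 mg is scored. VAS forms are completed "questionnaire electronically throughout the dose reduction process", and section d) treats the study as complete once a woman is off the drug, which leans against scoring; Table 1 does print weeks at 0 mg. Not every woman will reach 0 either. The plan provides for step-backs ("After the subject has been on the higher dose for one week we will re-initiate the dose reduction strategy to which she was assigned") and for stopping at the lowest tolerable dose. Entry is allowed up to 30 weeks' gestation, while an uninterrupted Magnitude taper takes 11 steps from 16 mg and 16 from 24 mg.

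**Conclusion.** The point holds as a minor improvement. Dosing versus Magnitude compares raw scores between non-randomised groups whose starting doses may differ, and nothing in the design or analysis handles that. An assumed gap of 2 to 6 mg in mean starting dose carries about 1 to 3 mg into the mean dose at the step. The within-woman contrasts also lack a dose term, but their imbalance is small.

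The documents do not allow the bias to be expressed in VAS points. They do not support a claim that any result would change sign or that the plan is invalid. The dose figures assume uninterrupted tapers from even starting doses. The simulated biases rest on assumed symptom patterns and show direction only.

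**What to change.** In section e):

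1. Analyse the weekly combined VAS score with a linear mixed model: a random intercept per woman and fixed effects for step type and pre-step dose.
2. For Dosing versus Magnitude, use only Dosing women on the Magnitude schedule, and add both group and starting dose. Do not rely on pre-step dose alone.
3. State whether weeks at 0 mg are scored. If they are, leave the step to 0 mg out of the step-type and group contrasts, report it separately, and add a sensitivity analysis that includes it.

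**Cost.** Wording only; the daily dose is already known, and dosing, visits and recruitment do not change. In the within-woman contrasts the dose term costs under 1% in standard error, or about 6% to 8% if the stop is also dropped. Starting dose raises the Dosing versus Magnitude standard error by roughly 1% to 15% in simulations with assumed inputs, more when the groups differ in starting dose. Pre-step dose also absorbs time and gestation, so its coefficient should not be read as a pure dose effect. Because Dosing women may choose the Frequency schedule, fewer than ten may enter the group contrast.

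### BID women may follow the Magnitude or the Frequency schedule, but section e) analyses the Dosing group only at 1 and 2 mg and only against Magnitude

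*Combined protocol and SAP*

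**What the plan says.** All references are to the combined protocol and SAP, Specific Aim 4.

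**Design (section d, Study Design, and Table 1).** Three groups of 10 are planned. On dosing frequency, "All subjects in the Magnitude and Frequency groups will be on TID or QID dosing". For the third group, on BID dosing, "we will compare tolerance to either the Magnitude or Frequency reduction schedule in women who are on a BID dosing regimen". The bullets that follow repeat this: "The Dosing group may follow the Magnitude (alternating 1 mg and 2 mg dose reductions weekly) or Frequency". Table 1 leaves the choice of schedule open in its Dosing column. No split, cap or allocation rule between the two schedules is given.

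**Analysis (section e, Statistics).** Two comparisons are named for the BID women. Within the group: "The comparison in the Dose group will be a comparison of the VAS scores during the 1 mg and 2 mg reductions". Between groups: "VAS scores in the Dose group will be compared to the VAS scores in the Magnitude group", at the 1 mg and at the 2 mg reductions. The contrast of 1- and 2-week intervals is named for one group only: "The comparisons in the Frequency group will be VAS scores between the 1 vs 2 week reductions". On sample size, section e) concludes that "a sample size of 10 in each group is sufficient to detect a difference in VAS scores between any of the comparison groups".

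**The concern.** The two analyses named for BID women presuppose the Magnitude schedule, yet the design does not require that schedule. For a BID woman who follows Frequency:

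- she has no 1 mg reductions, so she drops out of both 1 mg comparisons;
- she does have 2 mg reductions, so section e) as written puts her into the 2 mg Dosing versus Magnitude comparison, where her schedule differs from the comparator's as well as her dosing frequency;
- the contrast her schedule was built to give (1 versus 2 weeks) and the comparison with TID/QID women on the same schedule are not named.

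At stake is the second primary research question, whether dosing frequency influences adherence during reduction. Dosing versus Magnitude is the only BID versus TID/QID comparison that section e) names. If the gap stays, someone must decide which BID women enter which contrast after the split, and possibly the data, are known.

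**Working it through.** **Step 1. Steps available under each schedule.** Counting the changes between weeks in Table 1 (16 mg start):

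| Schedule | Weeks with a 1 mg drop | Weeks with a 2 mg drop |
|---|---|---|
| Frequency | none | 2, 4, 5, 7, 8, 10, 11, 13 (eight) |
| Magnitude | 2, 4, 6, 8, 10, 12 (six) | 3, 5, 7, 9, 11 (five) |

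Check: 8 × 2 = 16 and 6 × 1 + 5 × 2 = 16.

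**Step 2. Where a BID woman's data go under section e).**

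| Comparison named in section e) | BID woman on Magnitude | BID woman on Frequency |
|---|---|---|
| 1 vs 2 mg within Dosing group | contributes | cannot contribute (no 1 mg data) |
| Dosing vs Magnitude at 1 mg | contributes | cannot contribute |
| Dosing vs Magnitude at 2 mg | contributes, same schedule | contributes, different schedule |
| 1 vs 2 weeks | not applicable | not named for BID women |
| Dosing vs Frequency group | not applicable | not named |

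So the 1 mg comparisons have k BID women, where k is the number on Magnitude. The plan does not state k.

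**Step 3. Reproduce the plan's sample-size table.** Inputs from section e): combined score 120; reductions of 15, 20, 25 and 30%, that is 18, 24, 30 and 36 points; SD ~25. The plan states no alpha, sidedness, power or test, so these are inferred. A two-sample t-test (non-central t), one-sided 5%, 80% power and SD 25 gives 25, 15, 10 and 7 per group, which matches all four rows. Other unstated bases match too: two-sided 5% with SD 22 at 80% power, and 90% power with SD about 21.3 (one-sided) or 19.0 (two-sided). Only the first uses the SD that the plan gives, so it is used below.

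**Step 4. Illustrative power at 1 mg, Dosing (k) versus Magnitude (10), 30 points.** Non-centrality = 30 / (25 × √(1/k + 1/10)), with k + 8 degrees of freedom.

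| k | Non-centrality | df | Critical t | Power |
|---|---|---|---|---|
| 10 | 30 / (25 × √0.2) = 2.683 | 18 | 1.734 | 82.5% |
| 9 | 30 / (25 × √0.2111) = 2.612 | 17 | 1.740 | 80.5% |
| 5 | 30 / (25 × √0.3) = 2.191 | 13 | 1.771 | 66.6% |

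At k = 5 the difference detectable with 80% power is 36.0 points; 36 / 120 = 30%, against the plan's 25%. At k = 0 neither 1 mg comparison can be made.

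**Step 5. Within-group 1 versus 2 mg contrast.** This is paired in k women. With SD 25 in each condition and within-woman correlation r (assumed, because the plan gives none), the SD of the difference is 25 × √(2(1 − r)): 35.4 at r = 0, 25.0 at r = 0.5, 19.4 at r = 0.7. One-sided 5% power for 30 points:

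| r | k = 10 | k = 6 | k = 5 |
|---|---|---|---|
| 0 | 79.6% | 55.8% | 47.1% |
| 0.5 | 96.7% | 80.8% | 71.2% |
| 0.7 | 99.8% | 94.3% | 88.0% |

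The loss from a smaller k therefore depends heavily on r.

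**The case against.** **The wider comparison is documented.** Section d) says that tolerance to either schedule will be studied in BID women and that measures will be compared within and between groups. This shows intent and rules nothing out. It specifies no contrast, however, and does not change the sentences in section e) that do.

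**A woman on Frequency may still reach 1 mg steps.** Section d) lets a woman who stays intolerant after repeat attempts, and who wants to try again, choose another strategy. It would therefore be wrong to say that such a woman can never give 1 mg data. The route is narrow, and the data it yields come from women selected for intolerance.

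**The power loss can be overstated.** A reader might infer that 10 per group is enough at 1 mg only if all ten BID women choose Magnitude. That is true as a head-count, but not as a power threshold. Nine versus ten still gives 80.5% on the basis used here (79.9% on the two-sided SD 22 basis). The paired contrast reaches 80.8% with six women at r = 0.5. On the bases that match the table at 90% power, five versus ten keeps 78.5% (one-sided, SD 21.3) or 76.0% (two-sided, SD 19.0). This objection stands, and the point is not worded as a threshold.

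**The SD matters more than the split.** SD ~25 was read from graphs for the withdrawal scale alone, while 30 points is 25% of a sum over four scales. If the SD of the sum were 50 (assumption: four independent scales, 25 × √4), one-sided power would be 36.2% with 10 versus 10 and 27.2% with 5 versus 10. This stands too, so the figures here are illustrations only.

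**Conclusion.** Sections d) and e) do not match for the Dosing group and must be reconciled. This conclusion needs no assumption about SD, alpha or power; it follows from the schedules open to BID women and the step sizes in Table 1. As written, section e) mixes schedule into the 2 mg Dosing versus Magnitude comparison whenever a BID woman follows Frequency. It leaves her out of the 1 mg comparisons (barring a later change of strategy) and names no analysis of her 1- versus 2-week data.

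The statement that 10 per group suffices for every comparison does not describe the 1 mg Dosing comparisons. The size of the loss depends on a split that the plan does not give: on the illustrative basis, from 82.5% at k = 10 to 66.6% at k = 5.

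A reader might also infer that the sample size is sound provided all ten BID women follow Magnitude. The documents do not support that either, because no SD is given for the combined score on which the 25% difference is defined.

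The change is worth making before analysis. It is not a fatal flaw, because the loss is conditional on an unknown split.

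**What to change.** Change the wording of section e) only; doses and schedules stay as they are.

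1. Compare BID with TID/QID women on the same schedule: Dosing women on Magnitude versus the Magnitude group, at 1 mg and at 2 mg; Dosing women on Frequency versus the Frequency group, at the 1-week and at the 2-week reductions, descriptively if numbers are small. Classify each woman by the first schedule she follows, and use only the weeks before any switch.
2. Limit the within-group 1 versus 2 mg contrast to BID women on Magnitude, and name the 1- versus 2-week contrast for BID women on Frequency.
3. Report the actual n of each contrast. Replace the blanket sample-size claim with a statement that the 1 mg Dosing comparisons have fewer than 10 BID women unless all follow Magnitude, without implying that 10 is otherwise shown to be adequate.

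**Cost.** The women, visits and questionnaires are unchanged. There will be more contrasts, each smaller, and no power is regained at 1 mg. Matching on schedule removes the schedule mixing but not the confounding. BID versus TID/QID is each woman's existing regimen, not a randomised one; BID women may choose their schedule, whereas "Subjects on TID or QID dosing will be assigned to either the Frequency or Magnitude groups based on their current dosing".

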Since our focus is to assess whether the magnitude of the dose change, frequency of dose change and dosing frequency impact adherence during reduction, this pharmacodynamic study will be completed when the subjects are off BUP entirely or on the lowest tolerable dose. However, we will continue to see the subjects weekly or biweekly, monitor their adherence and continue to provide counseling sessions, as needed, until the 6-week postpartum visit. We will also evaluate peripheral blood mononuclear cells (PBMCs) as a surrogate marker of metabolic enzymes and transporters. The expression of drug metabolizing enzymes and transporters in the PBMCs will be correlated with the plasma concentrations of BUP and its major metabolites. Two maternal blood samples will be drawn for PBMC analysis; one during pregnancy and one in postpartum. The first sample will be drawn during the Pre-Study Screening; however, if this is not possible, it may be drawn at any time during pregnancy. The second sample will be drawn at 4-6 weeks postpartum, but as close as possible to the 6-week postpartum visit.

For subjects not enrolled in specific aim 3a or 3b, we will collect a cord blood sample at the time of delivery as well as maternal and newborn hair within 3 days of delivery, when possible. An additional cord blood sample (10 mL) will be drawn for genetic studies related to metabolizing enzymes, if the mother consents. The minimal amount of hair needed is 20 mg but we will ask for 100 mg which is still a very small amount. Hair will be removed from the mothers and baby's head (if consent is granted). Mother will decide where the hair will

be removed from her and her baby. The collection of these samples will be described in full detail during the consent process.

Note: Subjects that consent to participate in specific aims 3 (Parts 1 or 2) will already have the cord blood and hair samples collected as part of that specific aim. The collection of these biological samples only applies to those subjects not already enrolled in specific aim 3.

Table 1.

Dose Reduction Schedules if Start Dose is 16 mg Daily			
Group	Frequency	Magnitude	Dosing
Strategy	Reduce dose by 2 mg weekly then biweekly, repeat till dose=0 or at the lowest possible dose	Reduce dose by 1 and then 2 mg weekly, repeat above till dose=0 or at the lowest possible dose	May elect either the Frequency or Magnitude dose reduction schedule.
Dosing Frequency	QID or TID	QID or TID	BID
Dose			

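### The 1 mg vs 2 mg contrast is tested separately in the Magnitude and Dose groups, and dosing frequency separately at each step size; one pooled analysis would give one answer per question and the missing interaction

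*Combined protocol and SAP*

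**What the plan says.** Section e) Statistics of Specific Aim 4 lists its comparisons one at a time. For step size in TID/QID women: "The comparisons in the Magnitude group would be VAS scores between the 1 and 2 mg reductions". For BID women: "The comparison in the Dose group will be a comparison of the VAS scores during the 1 mg and 2 mg reductions". For dosing frequency: "VAS scores in the Dose group will be compared to the VAS scores in the Magnitude group both at the 1 and 2 mg reductions".

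Section d) Study Design sets 10 women per group. It allows the BID group to follow either reduction schedule, and Table 1 says the same: "May elect either the Frequency or Magnitude dose reduction schedule". Between 0 and 10 BID women will therefore be on the same alternating 1 mg and 2 mg weekly schedule as the Magnitude group.

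Section d) also says that measures will be compared within and across groups, without saying how. The document gives no pooled estimate, no step-by-group interaction, no primary comparison and no rule for multiple tests.

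**The concern.** The Magnitude-group and Dose-group comparisons of 1 mg with 2 mg estimate the same kind of within-woman contrast, and both bear on the magnitude part of primary question 1. Splitting them gives two verdicts from at most 10 women each, with no rule for what to conclude if they differ. Primary question 2 (dosing frequency) likewise receives two verdicts from the same women, one at each step size.

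The quantity that links the two questions is whether the 1 vs 2 mg difference itself differs between BID and TID/QID women. It is never tested. Without it, a significant result in one group and a non-significant result in the other cannot be interpreted: that pattern is common when the true effects are identical, and it is not evidence that dosing frequency matters.

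**Working it through.** **Inputs from the document.** The difference of interest is 25% of a summed score of 120, so 0.25 × 120 = 30 points (e) Statistics and its sample-size table). The SD is about 25, given for the withdrawal scale alone; none is given for the four-item sum or for a within-woman difference. There are 10 women per group.

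**Assumptions.** Two-sided 5%, and a correlation ρ between a woman's 1 mg and 2 mg scores. Neither is stated, so a range of ρ is shown.

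**1. The plan's own figure.** A two-sample t-test with SD 25, one-sided 5% and 80% power, for differences of 18, 24, 30 and 36 points, needs 25, 15, 10 and 7 per group. This matches all four rows of the table. The two-sided version needs 32, 19, 12 and 9. The table therefore appears to rest on a one-sided comparison of independent groups; at n = 10 the two-sided power of that test is 72%.

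**2. Step size, separate against pooled.** The SD of the within-woman difference is SDd = 25 × √(2(1 − ρ)). Power comes from the noncentral t with noncentrality 30√n / SDd, on n − 1 df for one group and n − 2 df when pooled with a group term. If both groups share the same true effect and each test has power p, the chance of opposite verdicts is 2p(1 − p); for example, 2 × 0.667 × 0.333 = 0.444.

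| ρ | SDd | Power, n = 10 alone | Pooled, n = 15 | Pooled, n = 20 | Two n = 10 tests disagree |
|---|---|---|---|---|---|
| 0 | 35.4 | 67% | 86% | 95% | 44% |
| 0.3 | 29.6 | 81% | 95% | 99% | 30% |
| 0.5 | 25.0 | 92% | 99% | >99% | 15% |
| 0.7 | 19.4 | 99% | >99% | >99% | 2% |

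**3. If only 5 BID women elect the Magnitude schedule.** The separate Dose-group test then has 31%, 41% and 53% power at ρ = 0, 0.3 and 0.5. Disagreement, p10(1 − p5) + p5(1 − p10), is 56%, 56% and 47%.

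**4. Without fixing an SD.** At 80% power the detectable effect is 1.00 SDd at n = 10, 0.78 at n = 15 and 0.66 at n = 20.

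**5. Sensitivity to the SD.** If the sum of four items had SD 50 (four independent items of SD 25: 25 × √4), power is 23%, 30% and 40% separately against 44%, 57% and 72% pooled at n = 20, for ρ = 0, 0.3 and 0.5.

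**6. False positives.** Two independent 5% tests give 1 − 0.95² = 9.75%. In simulation, the two correlated dosing-frequency tests give about 8% to 10%.

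**7. Interaction.** With 10 women per group its standard error is SDd × √(1/10 + 1/10) = 0.447 SDd. The pooled effect has SDd/√20 = 0.224 SDd, so the interaction interval is twice as wide.

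**8. Dosing frequency.** Averaging a woman's two step-size scores multiplies the standard error by √((1 + ρ)/2), which is 0.81, 0.87 and 0.95 at ρ = 0.3, 0.5 and 0.8. That is a reduction of 19%, 13% and 5%. For 10 vs 10 women, power rises from 72% at one step size to 88% at ρ = 0.3 or 83% at ρ = 0.5.

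**9. Form of the joint model.** Simulated case (all values assumed): 20 women, 5 weeks per step size, residual SD 15, no mean step effect. If the step effect varies between women with SD 5, 10 or 15, a model with only a random intercept rejects the true null about 8%, 15% and 24% of the time. A test on per-woman differences stays near 5%.

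**The case against.** The strongest objection is that regimen-specific results are a legitimate target. Section d) Study Design argues that more frequent dosing sustains plasma concentrations better, and the Dosing group exists to see whether tolerance differs on BID. The disagreement rates assume equal true effects, which that rationale does not take for granted. A pooled effect also averages over a mix of regimens set by which schedule BID women elect. This stands, and it is why group-specific estimates should be kept. It also strengthens the case for an interaction estimate, because the listed comparisons at each step size do not supply one.

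The separate tests may also be adequate. At ρ = 0.5 and SD 25 each has 92% power. With the one-sided test that the table implies, disagreement falls to 32%, 17%, 6% and under 1% at ρ = 0, 0.3, 0.5 and 0.7. This stands as a limit on size.

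The documents do not support four stronger readings that a reader might infer:

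- **That pooling brings more women to every question.** Each dosing-frequency comparison already uses both groups; only the 1 vs 2 mg contrast goes from 10 to up to 20 women.
- **That half of all verdict pairs will conflict.** That rate arises at a true effect of 0.66 SDd, which is simply the effect that the pooled analysis can detect. It is not the plan's effect.
- **That the investigators will report step size as mattering on one regimen only.** No section says so.
- **That pooling is free of bias because each woman is her own control.** That removes between-woman differences only. Steps always run 1 mg then 2 mg while the dose falls, in both groups, and pooling narrows the interval around the same contrast.

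**Conclusion.** The point holds as an inexpensive improvement to the analysis. For 1 vs 2 mg, at 30 points and SD 25 with two-sided 5%, pooling 20 women raises power from 67%–92% to 95%–over 99% for ρ between 0 and 0.5. It also replaces two verdicts that would disagree 44% to 15% of the time under a common true effect.

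These figures depend on assumed values of ρ and α and on an SD stated for a single scale. If ρ is high, the power gain is small; if the summed score is more variable, both approaches have less power. If no BID woman elects the Magnitude schedule there is nothing to pool. For dosing frequency the gain is one verdict and a 5% to 19% smaller standard error (ρ from 0.8 to 0.3). That contrast stays non-randomised, because group follows current dosing.

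**What to change.** In e) Statistics, replace the separate Magnitude, Dose and Dose-vs-Magnitude comparisons with one analysis of all women on the Magnitude schedule:

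1. For each woman, compute the mean weekly combined VAS score over her 1 mg steps and over her 2 mg steps.
2. Use the pooled within-woman difference, with a centred group term, as the single test of 1 vs 2 mg.
3. Report the group difference in that quantity, with its confidence interval, as the step-by-group interaction.
4. Use the group difference in each woman's average over both step sizes as the single dosing-frequency test.
5. Keep the group-specific estimates as descriptive results.

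The model-based counterpart is a mixed model with a random intercept and a random step-size slope, effect-coded step and group factors with their interaction, and a current-dose or week term for the fixed order and falling dose. A random intercept alone is not enough (item 9 of the check). With reference coding, the group coefficient would refer to one step size only. If the groups are unequal, state how they are weighted.

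The cost is analysis wording and a little programming, with no new patients or data. The downside is that the pooled step effect averages over regimens, while the interaction shown beside it will be imprecise.
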